This protocol describes the RIPCOM1 study and provides information about procedures for entering participants. Every care was taken in its drafting, but corrections or amendments may be necessary. These will be circulated to investigators in the study. Problems relating to this study should be referred, in the first instance, to the Chief Investigator.

This study will adhere to the principles outlined in the NHS Research Governance Framework for Health and Social Care (2^{nd} edition). It will be conducted in compliance with the protocol, the Data Protection Act and other regulatory requirements as appropriate.

INTRODUCTION

1. INTRODUCTION

1.1 BACKGROUND

Mitral regurgitation (MR) is one of the most prevalent valvular heart conditions in population based studies (1) and the hospital and outpatient patient population (2). The incidence of mitral valve surgery has been shown to be increasing in a European series (3) and the United States (4). One of the major driving forces has been an appreciation of the benefits of successful mitral valve repair over mitral valve replacement in terms of operative mortality, potential avoidance of lifelong anticoagulation and long term survival. This has resulted in an increase in mitral valve repair rates in Europe and the United States.

The current indications for surgery for MR include symptomatic status; asymptomatic status with echocardiographic features such as impaired left ventricular function or increased left ventricular dimensions; new onset atrial fibrillation or pulmonary hypertension; asymptomatic status with a high likelihood of durable repair and low co-morbidity (5). The limitation in strength of the current evidence base is reflected by the class of evidence being expert opinion (level C) for all of the above indications with the sole exception of symptomatic patients, which is level B.

The fulcrum point between asymptomatic status and symptomatic status at which patients would derive prognostic benefit and thus should be referred for surgery on prognostic grounds still remains unclear and controversial. Although elective mitral valve repair carries a low risk of mortality (4), it has been demonstrated that asymptomatic patients with severe degenerative MR can be safely followed up before becoming symptomatic or reaching cutoff values for left ventricular dimensions, size or pulmonary hypertension; with no significant difference with expected survival. As a result, prophylactic surgery for all patients with asymptomatic severe degenerative MR can not be recommended on prognostic grounds (6).

At the other end of the clinical spectrum, the increased operative mortality and worse long term prognosis of symptomatic patients is well proven. Patients with New York Heart Association Class III or IV status have excessive operative mortality and significantly increased mortality at 10 years (7). Both this study and another (8) have demonstrated that preoperative ejection fraction is an independent predictor of long term survival. Although this evidence base does not support prophylactic surgery on asymptomatic patients, it does highlight the importance of avoiding the long term sequelae of MR in causing symptomatic status or left ventricular impairment. Hence attention has turned to objective markers or investigations independent of symptomatic status that may be subjectively assessed in the early phases; to help identify patients who would prognostically benefit from earlier surgical intervention.

As a result of rheumatic fever being the most common etiology, mitral stenosis (MS) is the least common valvular lesion in the hospital population (2) and has a low prevalence rate in epidemiological studies (1) in industrialized countries. However, it still causes significant morbidity and mortality worldwide. The preferred treatment for severe mitral stenosis in those patients with favourable valvular anatomy is percutaneous mitral commissurotomy. In one single centre follow up, there was a low immediate risk of the procedure with 89% of patients obtaining good immediate results defined as a final mitral valve area greater than 1.5cm² without significant mitral regurgitation and a 20 year rate of good functional results of 30.2% (9).

[name] 22/12/16 16:42 Deleted: 2 [name] 22/12/16 16:43 Deleted: 1 [name] 22/12/16 16:43 Deleted: 9

Version 3, 31/12/2016 However, in those patients with unfavourable valvular anatomy; there are no randomised trials to guide the best timing of surgery. Survival benefit increases with more advanced symptoms, but surgical risk increases with pulmonary hypertension so it has been suggested to intervene when symptoms are more than mild, but before the development of pulmonary hypertension (10). An area of uncertainty exists in asymptomatic patients with severe MS or those with symptoms out of proportion with the severity of MS. Current guidelines suggest the use of stress echocardiography and intervention if the mean transmitral pressure gradient is greater than 15mmHg during exercise or peak pulmonary artery systolic pressure exceeds 60mmHg (11). However, this guidelines is based on level C evidence and there is no data comparing these parameters with objective measurements of exercise capacity and its relationship with operative risk or long term prognosis.

In summary, severe mitral valve disease is a common valvular pathology that causes a significant burden of disease in the United Kingdom and worldwide. Current guidelines for timing of operative intervention are mostly based on expert opinion rather than randomised trials or studies. There is currently no proven prognostic benefit from surgery on asymptomatic patients. Patients with significant symptoms benefit from surgery, but have worse long term prognosis than the general population. It is difficult to assess early or mild symptoms and there is no significant evidence base objectively measuring exercise capacity and its correlation with quality of life and markers of cardiac or respiratory function before and after surgery.

Pathophysiology of severe mitral valve disease

In the initial compensated phase of MR, there is eccentric hypertrophy of the left ventricle and enlargement of the left atrium to accommodate volume overload. As a result of the increased capacitance there is a normal pulmonary vascular resistance and transpulmonary pressure gradient. In the final decompensated phase, there is heart failure characterized by increase in left ventricular dimensions, elevation of left sided filling pressures, increase in transpulmonary pressure gradient and decline in biventricular contractile function (12). This is associated with progressive histological changes to the pulmonary vasculature which range from medial hypertrophy and intimal proliferation in small muscular pulmonary arteries to progressive fibrous vascular occlusion and arterial dilatation and the end stage of haemosiderin deposition and necrotizing arteritis (13). This in turn affects the alveolarcapillary unit and can increase impedance to gas transfer. From a clinical end point, this results in pulmonary hypertension and potentially reduced gas transfer factor.

Right heart catheterisation (RHC) is regarded as the gold standard for establishing a diagnosis of pulmonary hypertension and allows invasive haemodynamic assessment. Transthoracic echocardiogram allows a non-invasive assessment of pulmonary pressures by calculating transtricuspid pressure gradient using the modified Bernoulli equation and adding right atrial pressure. However, this method is restricted by the limitations of acquiring a continuous wave signal and severe tricuspid regurgitation (14). One metaanalysis comparing the accuracy of echocardiography and RHC in 29 studies reported modest correlation between the two methods and that RHC remains the gold standard. Of the 29 studies, only 8 evaluated cardiac disease, none evaluated a mitral disease cohort and the studies were subject to significant biases (15).

Although pulmonary hypertension is an important risk factor and indication for surgery, there is currently no prospective comparison of measurements on transthoracic echocardiogram and RHC. In addition, the changes in the histology of the left and right ventricle and changes in pulmonary function have not been related to changes in pulmonary haemodynamics.

[name] 22/12/16 16:42 Deleted: 2 [name] 22/12/16 16:43 Deleted: 1 [name] 22/12/16 16:43 Deleted: 9

Version 3 31/12/2016

1.2 RATIONALE FOR CURRENT STUDY

To identify objective markers of exercise capacity, cardiac or respiratory function that will demonstrate the earliest point at which patients with severe mitral valve disease derive prognostic benefit from surgery.

Patients with severe mitral valve disease and symptoms although gaining benefit from surgery have a worse long term prognosis and quality of life than the general population. There is currently no proven prognostic benefit for surgery on asymptomatic patients. Therefore there will be an objective point between the two ends of the disease spectrum at which patients will derive early prognostic benefit and enable a return to a normal life expectancy and quality of life.

2. STUDY OBJECTIVES

Primary objective

Correlation between objective measurements of exercise capacity on cardiopulmonary exercise testing with quality of life and measurement of cardiac function on transthoracic echocardiogram and cardiac MRI in severe mitral valve disease.

Secondary objective

1. The accuracy of transthoracic echocardiogram compared to right heart catheterization in measuring pulmonary artery pressures in a prospective severe mitral valve disease cohort.

2. Histological changes in the left and right ventricle in severe mitral valve disease.

The additional pre-operative investigations will be co-ordinated with the preassessment team to minimize changes to the normal patient pathway. If patients have already had pre-operative investigations required as part of the study protocol prior to enrolment, the data from these investigations may be used for the purposes of research.

Clinical history and examination- Patients will be reviewed at initial surgical consultation, 6-8 weeks after surgery and one year after surgery.

Right heart catheterisation- It is the usual gold standard practice at our institution for patients to have a right heart catheterisation before being referred for surgery. The few patients who have not had one before surgery will be referred to the Department of Pulmonary Hypertension at Hammersmith Hospital for this test to be performed.

Cardiac MRI- patients will have a T1 weighted non-contrast cardiac MRI. One strength of cardiac MRI over transthoracic echocardiogram is the ability to provide objective measurements of right heart function. Parameters measured will be left and right ventricular ejection fraction, cardiac chamber dimensions, patterns of myocardial fibrosis.

Cardiopulmonary exercise testing (CPET)- CPET is a quantitative and validated method of assessing cardiorespiratory function and exercise capacity with commonly measured variables including maximal oxygen consumption (VO2 max) and the clearance of carbon dioxide during exercise (Ve/VCO2). The patient's gaseous exchange is monitored during a 3 minute rest period, a three minute "rolling basal" period when they perform exercise on a bicycle with no load; and subsequently during the exercise phase when the work load increases at a rate of 30 Watts per minute. The exercise continues until the patient has to stop or predicted maximum heart rate is achieved.

Pulmonary function tests- Patients will have routine spirometry tests and also assessment of transfer factor (DLCO and KCO). It is normal practice for patients to have spirometry at preassessment clinic and those with abnormal spirometry or a significant history of respiratory disease to have transfer factor measured.

Transthoracic echocardiogram- It is normal practice for patients to have a transthoracic echocardiogram at preassessment clinic to assess biventricular function, dimensions and cardiac structural disease.

Quality of life questionnaire- At the preassessment clinic, patients will be asked to fill out a validated quality of life questionnaire (SF-36 health survey).

Intra-operative specimens

Heart muscle biopsies will be obtained at the time of clinically indicated heart surgery. Two small heart samples approximately 0.8 grams each or the size of a cooked rice grain will be taken from the left and right ventricle. The specimens will be preserved in formalin and processed and analysed at the Department of Pathology by a pathologist with a specialist interest in cardiac pathology. The samples will be fixed and analysed with haematoxylin and eosin for structure, Elastin van Gieson stain for elastin, Martius, Scarlet and Blue stain for fibrin, Picrosirius red stain for collagen, Perls' Prussian blue stain for iron, Periodic acid-Schiff stain for polysaccharides, Desmin stain for smooth muscle, CD68 for monocytes, CD45 for leucocytes, smooth muscle actin for smooth muscle and CD31 for vascular endothelium.

[name] 22/12/16 16:42 Deleted: 2 [name] 22/12/16 16:43 Deleted: 1 [name] 22/12/16 16:43 Deleted: 9

By correlating the results of the histological analysis with clinical markers such as left and right ventricle function and pulmonary hypertension, and the cardiac imaging on transthoracic echocardiogram and cardiac MRI this will enable us to grade microscopic changes in the myocardium throughout the spectrum of mitral valve disease from asymptomatic to symptomatic.

In addition, the results of the histological analysis will be the basis of further collaborative work with the Myocardial Function group at the Imperial Centre for Translational and Experimental Medicine.

Post-operative follow up

6-8 weeks- it is normal practice for patients to be reviewed at 6-8 weeks after surgery in clinic with clinical history and examination. Patients will be asked to fill in a quality of life questionnaire at this time.

6-9 months- Patients will have a repeat transthoracic echocardiogram, cardiac MRI, CPET, pulmonary function tests. A quality of life questionnaire will be mailed to patients with a self-addressed envelope.

12 months- it is normal practice for patients to be followed up at 12 months after surgery with clinical history and examination.

Review of investigations

All pre and post-operative investigations will be reviewed on an individual basis with the Chief Investigators and if there are any abnormalities, these and any additional investigations will be discussed with the patient. The patient's GP and referring cardiologist will be informed of any progress with the permission of the patient.

3.1 STUDY OUTCOME MEASURES

- 1. The accuracy of transthoracic echocardiogram compared to right heart catheterization in measuring pulmonary artery pressures in a prospective severe mitral valve disease cohort.
- Correlation between objective measurements of exercise capacity on cardiopulmonary exercise testing with quality of life and measurement of cardiac function on transthoracic echocardiogram and cardiac MRI in severe mitral valve disease.
- 3. Histological changes in the left and right ventricle in severe mitral valve disease.
- Pilot data on changes in exercise capacity and quality of life and relationship to transthoracic echocardiogram, cardiac MRI and pulmonary function tests early after mitral valve surgery.

4. PARTICIPANT ENTRY

4.1 PRE-REGISTRATION EVALUATIONS

Transthoracic echocardiogram showing severe mitral valve disease meeting the current indications for open heart surgery.

4.2 INCLUSION CRITERIA

Patients undergoing cardiac surgery for severe mitral valve disease with or without concomitant coronary artery bypass grafting or tricuspid valve surgery or atrial fibrillation surgery.

[name] 22/12/16 16:42 Deleted: 2 [name] 22/12/16 16:43 Deleted: 1 [name] 22/12/16 16:43 Deleted: 9

4.3 EXCLUSION CRITERIA

Age <18 years or >85 years, pregnancy, critical preoperative status with multi-organ dysfunction, emergency cardiac surgical intervention, unable to give informed consent or unwilling to participate in research, patients with definite contraindication for MRI would be excluded from the cardiac MRI element of the study, patients unable to take adequate biopsies due to technical difficulties would be excluded from the myocardial biopsy element of the study, other significant valve lesions requiring concomitant surgery.

4.4 WITHDRAWAL CRITERIA

Patients who develop a life expectancy limiting medical condition subsequent to enrolment will be withdrawn from the study. Patients will have the right to withdraw from the study at any time. Patients who lose capacity will be withdrawn from the study but data and tissue already collected with consent will be retained and used in the study with no further data or tissue collected.

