RIPCOM 1

The right ventricular pulmonary circulation in mitral valve disease study 1

Statistical methods

Version 1 31/12/2016 IRAS ID 199676

MAIN SPONSOR: Imperial College London FUNDERS: Applications to Heart Research UK, Rosetrees Trust and British Heart Foundation pending STUDY COORDINATION CENTRE: Department of Cardiothoracic Surgery, Hammersmith Hospital NRES reference: 199676

Protocol authorised by:

Name & Role	Date	Signature
[name]	31/12/16	
[name]	31/12/16	
[name]	31/12/16	

Statistical methods

Data are presented as mean \pm SD for continuous numerical variables and as count and percentages for categorical variables. Normality was assessed with Lilliefors (Kolmogorov-Smirnov) normality test: for consistency in reporting the data we have reported the numerical variables as mean \pm SD regardless their distribution. We compared the pre-operative characteristics, echocardiographic characteristics and CPET variables between class 1 and class 2 diagnosis with Student t-test for normally distributed numerical variables and Mann-Whitney (Wilcoxon) test for not normally distributed numerical variables. The comparison between categorical variables was conducted with Chi-square test or Fisher Exact test as appropriate. The CPET results before and after surgery have been compared using paired t-test or paired Wilcoxon test depending on the distribution.

Primary Outcome: reduced functional capacity at follow up

This was a per protocol analysis. To identify the predictors of reduced functional capacity we have run two different types of regression models. In the first model (linear regression) we have treated our outcome (VO2 % at follow up) as a numerical continuous variable. The predictors were evaluated trough a univariable analysis first and then a multiple model was run including those predictors that appeared to be significant at univariable analysis. The final model was obtained via a backward selection using AIC (Aikake Information Criterion) as criterion.

In the second model, the outcome was defined as a dichotomic variable that included a VO2% of $\leq 84\%$ and/or LVEF $\leq 50\%$ at follow up. To evaluate the predictors of

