this outcome we have run univariable and multivariable logistic regression model. In consideration of the fact that the overall number of events for this outcome was limited, the final multiple model was a parsimonious model developed using a meaningful selection of the variables that were considered relevant in previous published research (preoperative LVEF \leq 60 %, LVESD \geq 40 mm and ppVO2 % $\leq 84\%$) plus the class of surgical indication.

Correlation between TTE parameters and MRI parameters

Linear models have been run to compare some TTE parameters with the same MRI models.

Comparing changes in quality of life between class of indication of surgery Linear mixed effects models were fitted for longitudinal (repeated measures) outcomes (physical functioning and social functioning) adjusted for time, preoperative percentage predicted peak VO2, preoperative LVEDD and preoperative LVESD.

For each of the main outcomes a stepwise approach has been used to model the data: first, an unconditional means model was run to describe the data and to test the null hypothesis; then an Unconditional Growth Model to set up the slope has been run followed by a Conditional Growth model (to set up the intercept). The unconditional mean model determines if the intercept is different from zero and if there is subjectrelated variability. The unconditional growth model can have a fixed or a random slope: the fixed slope is based on the assumption that each individual in the dataset is following a similar pattern over time, while the random slope allows individual variability. Both models have been run to find out the best fitting model. The Conditional growth model is the final step and it is the complete final model adjusted for the covariates. All models were fitted using maximum likelihood methods.

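### Section 4.4 withdraws patients who develop a life-limiting condition after enrolment, which can bias the SAP's follow-up analyses towards patients who did well

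*Protocol*

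**What the plan says.** Protocol section 4.4 has three parts.

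- A compulsory rule: "Patients who develop a life expectancy limiting medical condition subsequent to enrolment will be withdrawn from the study".
- The patient's own right to leave at any time.
- A rule for loss of capacity: "Patients who lose capacity will be withdrawn from the study but data and tissue already collected with consent will be retained", with nothing further collected.

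The first rule does not define the condition, does not separate unrelated illness from consequences of the valve disease or surgery, and does not say what happens to data already held.

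The SAP sets "Primary Outcome: reduced functional capacity at follow up". It models VO2% as a continuous variable. In a second model "the outcome was defined as a dichotomic variable", met by VO2% at or below 84% and/or LVEF at or below 50% at follow-up. On the analysis population it says only "This was a per protocol analysis". Protocol section 3 (post-operative follow up) and section 6 place the repeat CPET, imaging and lung function tests at 6-9 months after surgery.

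**The concern.** The withdrawal rule operates between enrolment and measurement of the outcome, and its trigger is worsening prognosis. The protocol itself links prognosis to the quantities being measured. Section 1.1 reports that ejection fraction before surgery predicts long-term survival, and it describes the end of the disease course: "In the final decompensated phase, there is heart failure characterized by increase in left ventricular dimensions". A patient whose ventricle fails after surgery could reasonably be judged to meet section 4.4, and that patient is also likely to be an event in the SAP's binary outcome.

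If so, selection depends on the outcome. Mean follow-up VO2% would be too high, the event proportion too low, and the slope of VO2% on pre-operative markers too shallow. The before-after CPET comparison is exposed in the same way. The SF-36 mixed models are exposed to a lesser degree: they are fitted by maximum likelihood and can use pre-operative and 6-8 week responses, provided those are kept.

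**Working it through.** **No figure to reproduce.** The documents give 50 patients but no power calculation, event rate or withdrawal rate. What follows is illustration under stated assumptions.

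**Is the rule offset elsewhere?** Protocol section 8.2 keeps patients in follow-up and analysis, but only when they are given alternative treatment. Section 4.3 lets a patient miss the MRI or biopsy element and stay in the study, so partial participation is already accepted. The SAP has no missing-data method, no sensitivity analysis and no comparison of withdrawn with retained patients. Nothing overrides section 4.4.

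**Continuous outcome.** Assume that marker and follow-up VO2% are bivariate normal, standardised, with correlation r of 0.4 or 0.6 (assumed). Withdraw a fraction p = 2/50, 3/50 or 5/50 (4%, 6%, 10%; assumed). Let v be the variance of the outcome among those retained. If withdrawal depends only on the outcome:

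- retained slope / true slope = v / (r²v + 1 − r²)
- lowest values withdrawn, cut-point c with Φ(c) = p: mean shift m = φ(c)/(1 − p); v = 1 + c·m − m²
- random from the lowest third, c = −0.431: the mean of that third is −1.091 and its mean square is 1.470, so m = 1.091p/(1 − p) and v = (1 − 1.470p)/(1 − p) − m²

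| Who is withdrawn | Quantity | 2 of 50 | 3 of 50 | 5 of 50 |
|---|---|---|---|---|
| Unrelated to VO2% | slope loss; mean shift | 0; 0 | 0; 0 | 0; 0 |
| Random from lowest third | v | 0.978 | 0.965 | 0.933 |
| | slope loss (r = 0.6 to 0.4) | 1-2% | 2-3% | 4-6% |
| | mean shift | 0.05 SD | 0.07 SD | 0.12 SD |
| Exactly the lowest | v | 0.835 | 0.787 | 0.712 |
| | slope loss (r = 0.6 to 0.4) | 11-14% | 15-19% | 21-25% |
| | mean shift | 0.09 SD | 0.13 SD | 0.20 SD |

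Example: lowest 10%, r = 0.4 gives 0.712/(0.16 × 0.712 + 0.84) = 0.746, a loss of 25%.

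**Binary outcome, upper bound.** Suppose that all w withdrawn patients would have been events. The observed proportion is (events − w)/(50 − w). The final logistic model has four predictors (LVEF, LVESD, predicted peak VO2 and class of indication), so events per variable is (events − w)/4. With w = 3:

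| Assumed events | Full cohort | After withdrawal | Events per variable |
|---|---|---|---|
| 10 | 20% | 7/47 = 14.9% | 2.50 to 1.75 |
| 15 | 30% | 12/47 = 25.5% | 3.75 to 3.00 |
| 20 | 40% | 17/47 = 36.2% | 5.00 to 4.25 |

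The SAP already says that "the overall number of events for this outcome was limited", so the loss falls on a model with few events to begin with.

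**Odds ratio.** Take an assumed 11/25 against 4/25 events: (11/14)/(4/21) = 4.12. Losing 3 events, all from the high-risk group, gives (8/14)/(4/21) = 3.00. If the same fraction k of events is kept in both groups, (11k/14)/(4k/21) is still 4.12. The odds ratio is therefore distorted only when withdrawal of events differs between marker groups. The event proportion falls in either case.

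**The case against.** **Section 4.4 does not name heart failure.** A reader might infer that the protocol orders removal of patients with post-operative heart failure, pulmonary hypertension or surgical complications. The text does not say so. A narrower reading, such as a new unrelated cancer, is open, and the background passages concern natural history and pre-operative status. This stands: the rule can remove such patients, but it is not shown to do so. The SAP also reports limited events rather than none, so some poor outcomes were measured. The ambiguity is still a defect, since two investigators could apply the rule differently.

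**The large slope losses are a ceiling.** The 11-25% range needs the withdrawn patients to be exactly those with the lowest VO2%. Under milder selection the loss is a few per cent, which is small against sampling error with 50 patients. This stands.

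**Some data would be missing anyway.** Patients who die or cannot exercise have no follow-up VO2% whatever section 4.4 says, so the whole loss cannot be charged to the rule. This stands. It does not apply to patients who could have attended, or who could have given an echocardiogram or questionnaire.

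**Sparing ill patients research tests.** Most of the 6-9 month tests are additional to normal practice, so burden is a plausible motive. Letting a patient omit tests serves that motive without withdrawal.

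**Scope.** A reader might infer that the protocol's primary objective is compromised. It is a CPET correlation that the first aim in the study summary makes pre-operative, and post-operative change is described as pilot data. That objective is little affected if baseline data are kept.

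**Silence is not deletion.** Nothing says that this group's data are discarded. That is correct, but stating retention for one withdrawn group and not the other leaves the question open.

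**Conclusion.** The concern holds in a limited form. Section 4.4 contains a compulsory, undefined, prognosis-triggered withdrawal rule that acts before the SAP's primary outcome is measured, and the analysis plan has nothing to offset it. It may bias the follow-up VO2% and VO2%/LVEF analyses and the before-after CPET comparison towards patients who did well, and the SF-36 models less so.

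The documents cannot settle the size. For 2-5 of 50 withdrawn and an assumed correlation of 0.4-0.6, slope attenuation lies between about zero and 25%, with about 1-6% under moderate outcome-dependent selection; mean shifts lie between 0 and 0.20 SD. A firm statement that improvement is overstated, or that heart failure cases were removed, goes beyond the text. The change is still worth making: it alters who is analysed, and it costs little.

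**What to change.** In section 4.4, replace compulsory withdrawal for a life-limiting condition with wording to this effect: such patients remain in the study; follow-up investigations are done only where the patient is willing and able; all data and tissue already collected with consent are retained and analysed. Leave the patient's right to withdraw and the loss-of-capacity rule as they are.

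In the SAP, report the number of withdrawals with reasons and timing. Add a sensitivity analysis of the binary outcome that counts as an event any cardiac death, or inability to perform CPET for cardiac reasons, before the 6-9 month visit.

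Cost: one amended sentence, one extra analysis and no new procedures. Some retained patients will have incomplete CPET data, and the change cannot recover VO2% for those who die or cannot exercise.
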